- 2. to compare the responses to resourcefulness training, biofeedback, and education program of these caregivers with caregivers of persons with bipolar disorder (from parent study) on the three outcomes over time; and*
- 3. to explore similarities or differences between the two types of caregivers in terms of their need for intervention (determined by baseline cut scores on study measures) and preference for intervention (response at end of study). Family caregivers of persons with dementia will complete validated study measures at baseline and within one month following intervention.*

Background

Directions: Describe the relevant prior experience and gaps in current knowledge describing how it will add to existing knowledge. Include any relevant preliminary data.

Recent statistics show that nearly 35 million family members in the United States provide unpaid care to an adult with a disability or illness. Close to 72% of these 35 million family caregivers care for adults with psychological or behavioral conditions known to be highly distressing.

While family caregivers of persons with bipolar disorder, the focus of our parent study, exceed 10 million, the number of family caregivers of persons with Alzheimer's disease or related dementias is even greater. As the population >age 65 continues to age, the number of persons with Alzheimer's and other forms of dementia is expected to escalate. More than 15 million family members provide some form of care or assistance for the over 5 million American elders who have some form of dementia. Research shows that family caregivers provide more

than 18 billion hours of informal, unpaid care for elders with dementia, constituting an annual cost to the nation that surpasses \$221 billion. In addition, the paid costs associated with health care, long-term care, and hospice for persons with Alzheimer's and other dementias are estimated to be \$214 billion each year, making dementia one of the most costly chronic illnesses in our nation. Although Medicare or Medicaid may cover up to 70% of the expenses, family caregivers assume remaining costs by paying out-of-pocket, contributing to additional stress on them. Thus, the tremendous societal burden associated with Alzheimer's and other forms of dementia extends well beyond those who suffer from this devastating condition.

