| 2. Has not cared for a living family member for at least the last 6 months. |
| 3. Has knowledge of another family member in the same household enrolled in the study |
| 4. Currently pregnant |
| 5. Has a pacemaker |
| 6. Lives outside of the study area |

Number of Research Participants

Directions: Indicate the target number of research participants to be accrued locally, and, if this is a multi-site study, indicate the total number of research participants to be accrued across all sites.

Based on previous research by the PI and Co-Is, we conservatively estimate that ~20% of caregivers may not meet eligibility criteria. Thus, we will screen 125 participants to obtain the desired sample of size of 100.

Special/Vulnerable Populations

1. Indicate specifically if you will include each of the following special populations by checking the appropriate box:

- Adults unable to consent**
- Minors (infants, children, teenagers)**
- Wards of the state
- Foster Children
- Pregnant Women
- Neonates
- Neonates of Uncertain Viability
- Employees of CWRU or UHHS
- Prisoners
- Illiterate Individuals
- Non-English Speaking
- University Students

None

2. If the research involves individuals that are included in a special/vulnerable population, describe the additional safeguards included to protect the rights and welfare of the individuals for each population indicated.

If family caregivers who do not speak/understand the English language come forward with interest in participating and if they meet all other study criteria, we will make accommodations for translating the study measures and intervention materials or for having an interpreter provide appropriate explanations. If an illiterate individual comes forward with interest in participating and if they meet all other study criteria, we will make accommodations to dictate the consent form and all study questions. If a caregiver is an employee or student of CWRU, the consent form identifies participation in this research study as voluntary and if they choose not to participate, it will not affect their current or future relations with the university. No caregivers unable to consent will be enrolled. Adults unable to consent are only subjects to the extent that there is any identifiable information about them collected through the caregiver. They will not be present for any interventions or interactions.

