The primary study aim (Aim #1) is to examine differences across our three groups of family caregivers of persons with dementia on caregiver health outcomes from pre- to post-intervention. The underlying analyses for A1 are built around the repeated measures analysis of variance (RMANOVA). The primary analysis will be a three group × two time waves RMANOVA. These analyses will compare the three groups: 1) usual care (education), 2) resourcefulness, and 3) biofeedback across two time waves of health risks and physical and mental health outcomes. When using RMANOVA, one not only assesses mean differences across time, but also group differences and the interaction of time × group, which will allow us to test the trend of the means over time across the three groups. The RMANOVA, not only is used to determine if there are mean differences across the two time periods, it also uses orthogonal polynomial contrasts to determine linear trends of the means across time. Orthogonal polynomials are weights assigned to each time period that models a linear trend. RMANOVA will determine if these trends in the means are significant. A linear trend is indicated if there is a steady increase or decline in scores from the first time wave to the second time wave.

The second aim (Aim #2) identifies the responses to usual care (education), resourcefulness training, and biofeedback separately on the three health outcomes between the caregivers of persons with dementia sampled within the proposed administrative supplement with the caregivers of persons with bipolar disorder sampled in the parent study. This aim involves three separate analyses to compare the two groups of caregivers within each of the three treatment groups (education, resourcefulness training, and biofeedback) for each of the three health outcomes. For each intervention/treatment program, a two group by two time point RMANOVA will be used to determine differences within and between groups and the interaction of time × group. For example, one RMANOVA will examine differences between caregivers of persons with dementia and caregivers of person with bipolar disorders on health risks over two time points.

The third study aim (Aim #3), to explore differences between the two groups of caregivers in terms of their need for intervention (determined by baseline cut scores on study measures) and

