preference for intervention (response at end of study), as these outcomes are categorical (i.e., education group, resourcefulness training group, or biofeedback group), we will use chi square analyses to determine the extent to which caregivers of persons with dementia differ from caregivers of persons with bipolar disorder separately for their need group and for their preference group in health self-management interventions.

Confidentiality of Data

1. To maintain the confidentiality of the data:

- I will use a unique study identifier to code individuals' identifiable data and will store the master list separate from the study data..
- Other **(please explain)**

Provide a plan to destroy identifiers including how and when.

2. How are you storing your electronic data?

- UH Redcap
- CWRU Redcap
- Secure Research Environment (SRE)
- CWRU Box
- OnCore
- UH Secure Network Drive
- CWRU Secure Network Drive
- Other - List storage method and provide justification:

3. Storage location of the paper research data and documents, if applicable:

- Paper research data and documents will be stored in a double-locked secure environment in the following location:
France Payne Bolton School of Nursing study office

4. Will data be shared?

- Yes

1. List the exact data elements that will be shared:

2. Describe how data will be sent:

- No
- N/A

(Please note: if sharing data, please contact the UH Grants and Contracts Specialist or CWRU Tech Transfer Office to ensure the proper contracts/agreements are in place.)

HIPAA Authorization

Does this study collect, access, use, or distribute any Protected Health Information (PHI)?

- Yes No

If yes, indicate how HIPAA authorization will be obtained (check all that apply):

- HIPAA authorization is in the consent form

- Requesting a full or partial waiver of HIPAA for prescreening
- I will complete the Request for Waiver of HIPAA Authorization form. *See SpartaIRB Library*
- Requesting a full or partial waiver of HIPAA
- I will complete the Request for Waiver of HIPAA Authorization form. *See SpartaIRB Library*

Devices

- This is **not** device study. The protocol is considered non-therapeutic (non-therapeutic is defined as research not intended to diagnose, prevent, cure, mitigate, treat, etc. a disease or condition) by the FDA. *— You may delete the rest of this section.*

OR

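### Aim 3 asks how similar or different the two caregiver types are, but its only named method, a chi-square test, gives neither the size of a difference nor evidence of similarity

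*Combined protocol and SAP*

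**What the plan says.** The Objectives word the third aim as "to explore similarities or differences between the two types of caregivers in terms of their need for intervention", and go on to name preference for intervention as the second characteristic compared.

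The Data Analysis Plan restates it more narrowly: "to explore differences between the two groups of caregivers in terms of their need for intervention". Similarities are no longer mentioned. The outcomes are treated as three-category variables, "as these outcomes are categorical (i.e., education group, resourcefulness training group, or biofeedback group", and the method is given in one clause: "we will use chi square analyses to determine the extent to which caregivers of persons with dementia differ". The comparison is made "separately for their need group and for their preference group in health self-management interventions", so there are two tests, each on a table of two caregiver types by three categories.

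For this aim the document states no effect measure, confidence interval, significance level, power calculation, similarity criterion or rule for reading a non-significant result. The size of the parent-study sample is not given.

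**The concern.** The question and the method do not match. The plan asks the chi-square test to determine an extent, but the test statistic and its p-value combine the size of the difference with the number of people studied. The same percentages can give a large p-value in a small sample and a small one in a large sample. Nor can the test support the similarity half of the aim: failing to reject equality is not evidence of equality, least of all when the samples are modest.

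The Background says that no comparative studies of these two caregiver types have been published, so readers will look to Aim 3 for how far need and preference differ. If the analysis goes no further than the named test, they will not find out. A non-significant p-value would leave open whether the groups are close or the study was too small to tell.

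**Working it through.** **The plan's own figure.** Aim 3 has no sample-size or power figure to reproduce. The only derivable size is the screening number in Number of Research Participants: with about 20% ineligible, 100 / (1 − 0.20) = 125. This matches "Thus, we will screen 125 participants to obtain the desired sample of size of 100".

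**Inputs**
- Dementia caregivers: 90, the number that Study Design/Procedures gives as receiving an intervention or usual care. The target of 100 is used as a check.
- Parent-study caregivers: not stated; range 90 to 300 assumed.
- Alpha: not stated; 0.05 assumed.
- Categories: three, from the Data Analysis Plan. Rates are not stated; one third each is assumed in the bipolar group.
- True difference: one category is higher by *d* in the dementia group, with the loss spread evenly over the other two.

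**Power of the test.** With group sizes n₁ and n₂, category probabilities p and q, and pooled m = (n₁p + n₂q)/(n₁ + n₂), the noncentrality is λ = n₁Σ(p − m)²/m + n₂Σ(q − m)²/m. Power is the probability that a noncentral chi-square with 2 df and noncentrality λ exceeds 5.991.

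Example, *d* = 10 points, 90 vs 90: p = 43.3/28.3/28.3%, q = 33.3% each, m = 38.3/30.8/30.8%.
λ = 180 × (0.05²/0.3833 + 2 × 0.025²/0.3083) = 180 × 0.01058 = 1.90, so power is 0.216.

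| True shift | Power, 90 vs 90 | Power, 90 vs 300 | Non-significant |
|---|---|---|---|
| 10 points | 0.216 | 0.323 | 68% to 78% |
| 15 points | 0.433 | 0.635 | 37% to 57% |
| 20 points | 0.677 | 0.876 | 12% to 32% |

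Placing the shift in the bipolar group instead changes little: at 90 vs 300, power is 0.308 for 10 points and 0.606 for 15. A simulation at 90 vs 100, with the shift in the bipolar group, gave 0.22 and 0.47, against 0.225 and 0.451 by formula.

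**Does the unknown parent size matter?** With an unlimited parent sample, the 10-point noncentrality becomes 90 × (0.10² + 2 × 0.05²)/(1/3) = 90 × 0.045 = 4.05, and power is about 0.42. With 100 dementia caregivers it is 100 × 0.045 = 4.5, and power is about 0.46. For a shift of this kind, the dementia sample sets the limit.

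**Precision of one category difference.** At rates near one third the 95% half-width is 1.96 × √[(2/9)(1/n₁ + 1/n₂)]:
- 90 vs 90: 1.96 × √(0.2222 × 0.02222) = 13.8 points.
- 90 vs 300: 1.96 × √(0.2222 × 0.01444) = 11.1 points.

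**Sensitivity to the pattern of the shift.** If the whole loss falls on one other category, the test is more powerful. For 10 points at 90 vs 90, λ = 180 × (0.05²/0.3833 + 0.05²/0.2833) = 2.76 and power is 0.30. For 15 points, power is 0.61 to 0.79 over the same parent sizes, and for 20 points 0.88 to 0.97.

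**The case against.** The strongest reply is that this is a short section in an institutional template, about an exploratory third aim. The counts behind a two-by-three table give the percentages anyway, and nothing limits the report to a p-value. That is fair, and it keeps the point modest. It does not remove it: the plan assigns the task of determining extent to a test that cannot do it, and names nothing else.

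A reader might infer three stronger things, none of which the documents support.

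- *That the investigators will report non-significance as similarity.* No rule says so, and the Data Analysis Plan speaks only of differences. What can be said is that the plan contains no safeguard.
- *That sizeable differences will usually be missed.* On the stated assumptions this holds for 10-point shifts. For 15 points it depends on the parent size and on the pattern of the shift, and a 20-point shift would usually be detected.
- *That similarity within 10 points could never be shown.* This rests on rates near one third and on a 95% interval. With rates near 10%, the 95% half-width is 8.8 points (90 vs 90) to 7.1 (90 vs 300). At one third, the 90% interval used with two one-sided tests has a half-width of 9.3 points at 90 vs 300. The chance of success would be low, but it is not ruled out.

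Nor does any section say that Aim 3 decides whether findings carry over from one caregiver type to the other. Need is measured at baseline, so that comparison may have closer to 100 dementia caregivers than 90; with 100, power for a 10-point shift is 0.225 to 0.346, which changes little.

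**Conclusion.** The point holds as a mismatch between question and method. The Objectives ask about similarities or differences, the Data Analysis Plan asks for the extent of difference, and the one named test supplies neither. That part rests on the text alone.

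The size is illustrative, because alpha, category rates and the parent sample size are all assumed. Within that range, a difference of 10 points in one category would more often than not be non-significant, and an interval around an observed difference would extend roughly 11 to 14 points either way. A non-significant result would therefore be weak evidence of similarity. Since the aim is exploratory and not primary, this is a worthwhile correction and not a threat to the trial's main conclusion.

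**What to change.** Amend the Aim 3 paragraph of the Data Analysis Plan so that:

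- the main output, for need and for preference separately, is the percentage in each category by caregiver type, the difference (dementia minus bipolar) with its 95% confidence interval, and Cramer's V;
- the chi-square test is kept as a supporting analysis;
- one sentence states that a non-significant result will not be reported as similarity.

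The aim should also be worded the same way in the Objectives and in the Data Analysis Plan, since only the former mentions similarities.

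A pre-specified equivalence margin is optional. If one is wanted, it should be fixed before the two samples are compared, and its demands should be understood. For one category near one third, with two one-sided 5% tests, 80% power and no true difference, the number per group is 2 × (2/9) × (1.645 + 1.282)² / margin²: about 381 for a 10-point margin, 170 for 15 and 96 for 20. With equal groups of 90 to 100, only a margin of about 20 points is realistic.

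The cost is a few sentences and a short table, with no new data. The conclusion may be less definite than a verdict of significant or not significant.

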
Following informed consent, research staff will collect detailed contact information and schedule the first data collection session. The data collection for caregivers sampled involves two structured face-to-face sessions with data collectors. Data will be collected at baseline (T1) and within one month after the 4-week intervention (T2). Measures include dementia symptoms, caregiver reactions, caregiving involvement, dementia knowledge, resourcefulness, heart rate

variability, health risks, and health outcomes, comprising the 156-item questionnaire. Demographic information will also be collected (e.g. occupation, annual income, education, and questions about the care recipient such as age, number of years diagnosed with dementia, specific diagnoses, and questions related to the participant's caring of their family member with dementia). Research assistants will encourage caregivers to respond to items displayed on an iPad/ tablet as they wish, ensuring there are no right or wrong responses. At the first data collection session, the study participant will receive a resource list for Dementia Care support and services in Cuyahoga and surrounding counties.

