COVID-19 remote modification – Beginning in July 2020, participants will provide e-consent via REDCap vs. written consent in person. If a person does not have email or would prefer to sign a paper consent form, two copies of the consent form will be mailed to their home, with instructions to sign and date both, and return one copy to the study office with the addressed and stamped envelope that is also provided (see page 9). Current participants will re-consent electronically. Enrolled study participants will have the option to download a copy of the consent form for their records, or it can be mailed / emailed to them (participant preference).

Updated COVID-19 Modifications June 2021: If an in-person data collection session is scheduled, the data collector may obtain signed informed consent at that time (6/30/21).

The two face-to-face interviews will instead consist of two remote data collection session. We will use phone (Google voice), Zoom (computer video), and/or email to complete the data

collection. For phone or video data collection, an email will be sent, if possible and requested, to participants with the answer response choices for each survey (this can also be sent by mail). If we are using phone for data collection, the Research Assistant (RA) will ask the participant each question and record the responses in our REDCap Surveys project. If collecting data using Zoom video, the RA will share the screen of the REDCap Surveys project, and record the answers for the participant as they review each survey question. If neither of those two options are available for the participant (e.g., limited phone minutes, inability to use Zoom), and/or email is preferred, the study may email the REDCap surveys to study participants for them to complete on their own at an agreed upon date / time (similar to in-person appointment); in this instance, the RA can be available to answer questions or clarify information as needed, by phone or email. It may be that none of these options will work for a study participant, in which case we will consider that data “missed” if we cannot wait to collect the data in person at a later date (when we resume normal study activities). The precise method(s) will depend on the ability and resources of the study participant. We will contact active participants with Zoom/ phone instructions, by phone/text and/or email, as needed, and we will record the methods used for each data collection done remotely.

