If no direct benefit, state the potential benefit to society or others. *Do not list compensation.*

Withdrawal of Research Participants

Directions: Describe the anticipated circumstances under which research participants will be withdrawn from the research without their consent. Also include the procedures that will be followed when a research participant withdraws or are withdrawn from the research, including partial withdrawal from procedures with continued data collection.

- N/A

Participants have the option of withdrawing from the study at any time and can request that no further information be shared about them from that point on. If a study participant withdraws consent to participate in the study, a research team member will notify the project manager to complete end of study documentation.

The project manager will review cases regularly with research staff to determine which study participants should be withdrawn from the study. Research participants will be withdrawn from the research without their consent if they are non-responsive to phone calls, emails, texts, or letters and considered lost to follow up.

Data that were collected prior to a study participant's withdrawal will be de-identified and still be used in the data analysis for the study. After withdrawal, no further data will be collected for that participant.

Alternatives to Participation

Directions: List other options to participation. If subjects will be compensated with extra course credit, the course instructor offering extra course credit must provide alternatives to earn extra course credit. The alternative assignment must require equal or less time and effort for the same amount of earned extra credit that you can earn through participation in research. If there are other available clinical treatments, what would be included if a subject continued on standard of care therapy. If there is a viable alternative you must list it in the consent.

- The alternative is for research subjects not to participate.

Costs to Research Participants

- There are **no** costs to research participants or their insurance companies (there are no clinical visits or billable procedures.) – *You may delete the rest of the section.*

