- d) Verification of source documents – This study does not involve printed or written documents; data will be collected through electronic data capture using REDcap software and then downloaded directly into SPSSPC files. Heart rate variability data will be downloaded from the assessment device and transcribed into the SPSSPC files. These sources will not include any data that would be personally identifiable.*

The SMC will review 1) all causes of mortality (e.g., caregiver death); 2) issues with participation (e.g., numbers and reasons for withdrawing from the study or refusing interventions, etc.) as well as recruitment refusal (percent and reasons) and subject attrition (percent and reasons); 3) missing data (including whether there are systematic patterns or whether data are missing at random); and 4) errors in data entry (which are expected to be minimal given the use of software for data collection with direct download into SPSS). In addition, differential attrition from the intervention groups (including the control and usual care groups, and the groups assigned to intervention based on need or personal preferences) will be monitored.

If concerns or problems are identified by the SMC, they will be reported to the IRB and NINR/NIH via email by [name] and [name], respectively, within 3 business days after they are identified. If there are recommendations made by the SMC, the action plan for response or notice of any actions taken by the IRB regarding the research and any responses to those actions will be provided to NINR Officials within 2 weeks.

e) Investigator compliance – Compliance of the investigators and all research team members who will have access to the data will be monitored annually. All research team members will be CREC certified; the CWRU intranet hosts a website where verification of compliance with continuing education for all investigators and team members can be evaluated.

2.) Reviewing and Reporting Adverse Events/unanticipated problems

1. Event identification

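### The two-wave RMANOVA leaves out caregivers without T2 and no missing-data method is given, so their T1 data do not enter Aims 1 and 2; the group comparison is exposed to bias if T1-related loss differs between arms or the effect varies with T1

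*Combined protocol and SAP*

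**What the plan says.** All references are to the combined protocol and SAP.

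- *Withdrawal of Research Participants*: data gathered before withdrawal "will be de-identified and still be used in the data analysis for the study". The section adds: "After withdrawal, no further data will be collected for that participant". Study staff also withdraw caregivers who are "non-responsive to phone calls, emails, texts, or letters and considered lost to follow up".
- *Study Design/Procedures*: there are two measurement waves, T1 at baseline and T2 within a month of the end of the four-week intervention. Under the COVID-19 modification, survey data that cannot be obtained by any route count as missed. HRV data that cannot be scheduled count as missing for that wave.
- *Data Analysis Plan*, Aim 1: "The primary analysis will be a three group × two time waves RMANOVA". It is described as a method in which "one not only assesses mean differences across time, but also group differences and the interaction of time × group". Aim 2 uses a two-group by two-wave RMANOVA within each intervention. Aim 3 compares baseline need and end-of-study preference by chi-square.
- *Provisions to Monitor the Data to Ensure the Safety of Research Participants*: data are "downloaded directly into SPSSPC files". The safety committee reviews missing-data patterns and differential attrition. No consequence for the analysis is attached to that review.

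The documents name no analysis population, intention-to-treat rule, imputation, mixed model, T1 adjustment or sensitivity analysis.

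**The concern.** With two waves, the time × group test of an RMANOVA is the same as an ANOVA of change scores. A caregiver with T1 only has no change score and drops out. The plan never says that cases will be deleted; this follows from the method it names. The statement about retained data is therefore not met for Aims 1 and 2.

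The concern goes beyond lost numbers. Caregivers with high T1 distress tend, on average, to move back toward the mean at T2. If more of them are lost from one arm, the completers in that arm start lower and show less of this movement. The arms then differ in mean change even if the interventions do nothing, and the comparison is no longer between the groups as randomised.

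**Working it through.** **The plan's own figure.** The only sample-size arithmetic is the screening number: 100 / (1 − 0.20) = 125, which reproduces exactly. It does not bear on this point. The documents give no dropout rate, SD, T1–T2 correlation, alpha or effect size.

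**Assumptions (none from the documents).** T1 and T2 have SD 1, and higher scores mean more distress. The correlation ρ is 0.3, 0.5 or 0.7. Loss depends on T1 only. There are about 33 caregivers per arm (100 / 3, equal allocation).

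**Formula.** Write T2 = a_g + ρ·T1 + e in arm g, and let m_g be the mean T1 of that arm's completers, where all randomised caregivers have mean 0. The completers' mean change is a_g + (ρ − 1)·m_g. Hence:

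- bias in the difference in change between arms 1 and 0 = (ρ − 1)(m_1 − m_0);
- bias in the time effect = (ρ − 1) × (mean of m_g over arms).

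**Case 1: same loss and same dependence on T1 in every arm.** Here m_1 = m_0, so the time × group bias is zero. The time effect is still biased. At 20% loss with log-odds 1 per SD of T1, m = −0.173; with ρ = 0.5 the bias is (−0.5)(−0.173) = 0.087 SD.

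**Case 2: 20% versus 5% loss, no treatment effect.**

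- Smooth loss (log-odds 1 per SD, by numerical integration): m = −0.173 and −0.047, a difference of −0.126. Multiplying by (ρ − 1) gives 0.088, 0.063 and 0.038 SD for ρ = 0.3, 0.5 and 0.7.
- Most distressed leave first: m = −φ(z)/(1 − loss), where z is the normal quantile at 1 − loss. This gives −0.350 and −0.109, a difference of −0.241. The bias is 0.169, 0.121 and 0.072 SD.

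**Case 3: equal 20% loss, related to T1 in the active arms only.** The bias is (ρ − 1)(−0.173 − 0) = 0.087 SD at ρ = 0.5. Over 10–30% loss and ρ of 0.3–0.7 it runs from 0.03 to 0.18 SD.

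**Case 4: equal T1-dependent loss, effect changing by 0.2 SD per SD of T1.** Completers' mean T1 is −0.091 at 10% loss and −0.253 at 30%. The contrast misses the average effect in all randomised by 0.2 × 0.091 = 0.02 to 0.2 × 0.253 = 0.05 SD.

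**Bias against sampling error.** In Case 2 the completers number 33 × 0.80 = 26.4 and 33 × 0.95 = 31.35. Ignoring the slight change in variance among completers, SE = √[2(1 − ρ)(1/26.4 + 1/31.35)] = 0.31, 0.26 and 0.20 SD for ρ = 0.3, 0.5 and 0.7. With an assumed two-sided 5% test and a normal approximation, P(|Z + bias/SE| > 1.96) is about 5.4–5.9% for smooth loss and 6.4–8.4% for top-tail loss.

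**What other methods recover.** Simulation with 3 × 33 caregivers, 8,000 runs, ρ = 0.5, true contrast −0.50 and log-odds slope 1:

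| Loss pattern | RMANOVA, completers | ANCOVA on T1, completers | Mixed model, all T1 |
|---|---|---|---|
| 20%, same in all arms | −0.500 | −0.499 | −0.500 |
| 20%, T1-related in active arms only | −0.412 | −0.498 | −0.499 |
| 30% active vs 10% education | −0.420 | −0.503 | −0.503 |
| 20%, opposite T1 dependence | −0.328 | −0.501 | −0.501 |

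**Precision without any loss.** The contrast variance is proportional to 2(1 − ρ) for change scores and to 1 − ρ² when T1 is used as a covariate or its mean is held common across arms. The ratio is (1 + ρ)/2, or 65%, 75% and 85% for ρ = 0.3, 0.5 and 0.7.

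**The case against.** The retained-data sentence answers an ethics-template question on withdrawal. It does not promise that every value enters the primary model. A reader might infer that it flatly contradicts the analysis plan; the documents do not support that, because T1-only data have a possible use in Aim 3, where need is set by baseline cut scores. This stands: the gap is a missing rule for Aims 1 and 2.

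A reader might also infer that any loss related to T1 distress biases the comparison of arms. That does not follow. When rate and dependence are the same in all arms and the effect does not vary with T1, the bias in the time × group contrast is zero.

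The sizes rest on assumed loss rates, and sampling error dominates them at this sample size. That also stands. The study-procedures section mentions 90 caregivers receiving an intervention or usual care against a target of 100. Reading that gap as 10% dropout would be a guess.

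HRV is listed apart from health risks and health outcomes, so missing HRV cannot be counted against Aim 1 on this text.

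Finally, ANCOVA of T2 on T1 removes the same bias in the Aim 1 arm contrast, so the mixed model is not the only adequate choice. None of this supplies a missing-data method or brings a T1-only caregiver into the RMANOVA.

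**Conclusion.** The point holds in a limited form. The named analysis for Aims 1 and 2 uses completers only, no alternative or analysis population is stated, and T1 data from withdrawn caregivers do not enter those aims. The time effect is biased whenever loss depends on T1. The comparison of arms needs a further condition: loss that differs between arms in rate or in T1 dependence, or an effect that varies with T1.

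Under the assumed 20% versus 5% loss, the bias is modest and would seldom change a conclusion by itself. Other assumed patterns are worse: with opposite T1 dependence at 20% loss, a true −0.50 becomes −0.33. Whether any such pattern will occur cannot be judged from the documents. The change is still worth making because it costs almost nothing, makes the retained-data statement true for Aims 1 and 2, and gains precision for Aim 1 even without loss.

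**What to change.** In the *Data Analysis Plan*, replace the RMANOVA for Aims 1 and 2 with a likelihood-based linear mixed model (SPSS MIXED) with wave, group and their interaction. Use every available T1 and T2 value from all caregivers in their assigned arm, including those with T1 only, and state this as the analysis population. For Aim 1 only, hold the T1 mean common across arms, which randomisation justifies. Do not do so for Aim 2, where the two caregiver types are not randomised.

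ANCOVA of T2 on T1 is an acceptable alternative for the Aim 1 arm comparison, but it does not use T1-only data and so would leave the retained-data statement unmet there. A sensitivity analysis for loss that depends on unobserved T2, such as shifting missing T2 values by arm, is optional; its range should be set in advance.

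The cost is a few lines of plan text and slightly more programming, with no extra participants or visits. Estimates may differ slightly from the RMANOVA contrasts. The correction holds only if loss depends on observed data.
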